5.1 Self-Monitoring and Reporting

Nurses guide patients to record their status weekly using the "Patient Self-Monitoring Record Form." The nursing team regularly collects this feedback data.

Table 3: Patient Self-Monitoring Record Form

Date	Type of Musculoskeletal Symptoms	Symptom Location	Start and End Time	Duration	VAS Score	Relief Measures	Remarks

Note: **VAS score** ranges from 0 to 10, where 0 indicates no pain and 10 indicates severe pain.

Instructions for Completion:

- China (Shanghai, Dali): Patients enter self-monitoring data through the app platform. By selecting “Symptom Monitoring” on the app, a musculoskeletal symptom record form will automatically pop up. Patients enter information sequentially to ensure accuracy and completeness. The system automatically saves and submits data to the nursing team for timely evaluation and care plan adjustments.
- Indonesia: Patients use the "Patient Self-Monitoring Record Form" for manual recording. Each week, they fill out the form, documenting symptom type, location, start time, duration, VAS score, and relief measures. Patients submit the completed form to the nursing team on time.

5.2 Diet and Nutrition Management

5.2.1 Daily Vitamin D Supplementation: It is recommended that patients take daily vitamin D supplements.^[1]

- For patients aged 18 to 50 with limited sun exposure, a daily intake of 1500-2000 IU of vitamin D is advised.
- For patients over 50, 1600-2000 IU is recommended to maintain serum 25(OH)D levels ≥ 30 ng/mL.^[2]

5.2.2 Omega-3 Fatty Acid Intake: Patients are encouraged to consume foods rich in omega-3 fatty acids^[3] (e.g., salmon, flaxseed oil, fish oil supplements).

5.2.3 Weight Management for Obese Patients: Patients with obesity (BMI ≥ 30) are advised to engage in weight management.^[3]

5.3 Exercise and Rehabilitation

Patients are instructed to follow the standardized exercise and rehabilitation regimen^[1, 4-6], with specific movements available in video format.

[figure not shown]

Figure 1: Exercise Demonstration Video Screenshots

Table 4: Standardized Exercise Rehabilitation Program

Aerobic Warm-up
Frequency: 5-7 times per week
Intensity: 60%-70% of maximum heart rate (220-age); RPE 3-4
Duration: 30-45 minutes
Repetitions: 5-10 times per set
Aerobic Warm-up for Young Group
Marching in place
Full-body stretch
Jumping jacks
Side steps with arm circles

Squat with alternating punches

Aerobic warm-up for the elderly group		
Marching in place		
Full-body stretch		
Full-body stretch		
Chest expansion exercise		
Abduction exercise		
Overhead reach		
Lateral movement		
Hip extension exercise		
Calf raises		
Functional Training		
Frequency: 3-5 times per week		
Intensity: RPE 3-4		
Duration: 15-30 minutes		
Repetitions: 8-12 times per set		
Location	Content	Nerves, Muscles, Joints
Hand	Hand functional exercise	Quadriceps, Hamstrings, Gastrocnemius, Soleus, Gluteus Maximus, Hip Flexors
	Wrist rotation	Flexor Carpi Radialis, Flexor Carpi Ulnaris, Extensor Carpi Radialis Longus, Extensor Carpi Radialis Brevis
Arm	Active posterior deltoid stretch	Deltoid (posterior fibers)
	Arm pull down stretch	Triceps Brachii, Latissimus Dorsi
	Active triceps stretch	Triceps Brachii
Shoulder	Arm flexion with shoulder circles	Biceps Brachii, Deltoid, Rotator Cuff muscles
	Shoulder extension with reach	Deltoid, Latissimus Dorsi, Trapezius
	Hands behind head	Trapezius, Deltoid, Rhomboids
	Prone Y extension	Trapezius, Rhomboids, Deltoids
	Wall slides	Deltoids, Trapezius, Rotator Cuff muscles
Hip and leg	Wall sit	Quadriceps, Hamstrings, Gluteus

Back	Standing left thigh stretch with wall support	Maximus Quadriceps
	Bent-over deadlift	Erector Spinae, Gluteus Maximus, Hamstrings
	Lunge stretch	Quadriceps, Hamstrings, Gluteus Maximus
	Seated butterfly stretch	Adductor muscles, Sartorius
	Flat back exercise	Erector Spinae, Rectus Abdominis
	Double knee to chest	Rectus Abdominis, Hip Flexors
	Supine knee touch	Rectus Abdominis, Hip Flexors

Table 5: Exercise Demonstration Table

Major Category	Sequence Number	Body Position	Exercise Name	Exercise Image	Target Joint
Warm-Up for Young Group	1	Frontal	Marching in place		Shoulder, Hip, Knee
	2	Frontal	Full-body stretch		Elbow, Shoulder, Hip

	3	Frontal	Jumping jacks		Elbow, Shoulder, Hip
	4	Frontal	Side steps with arm circles		Elbow, Shoulder, Hip
	5	Lateral	Squat with alternating punches		Shoulder, Hip, Knee
Warm-Up for Elderly Group	1	Frontal	Chest Expansion Exercise		Wrist, Elbow, Shoulder

2	Frontal	Chest Stretch Exercise		Elbow, Shoulder, Hip
3	Frontal	Abduction Exercise		Elbow, Shoulder, Hip
4	Frontal	Overhead reach		Elbow, Shoulder, Hip
5	Frontal	Lateral movement		Ankle, Hip, Shoulder

	6	Lateral	Hip extension exercise		Shoulder, Hip, Knee
	7	Lateral	Calf raises		Toe, Ankle, Knee
Shoulder Exercises	1	Frontal	Arm flexion with shoulder circles		Elbow, Shoulder, Hip

	2	Frontal	Shoulder extension with reach		Wrist, Elbow, Shoulder
	3	Frontal	Hands behind head		Elbow, Shoulder, Hip
	4	Frontal	Prone Y extension		Elbow, Shoulder, Hip

	5	Frontal	Wall slides		Elbow, Shoulder, Hip
Arm Exercises	1	Frontal	Active posterior deltoid stretch		Wrist, Elbow, Hip
	2	Lateral	Arm pull down stretch		Elbow, Wrist, Pinky Finger
	3	Frontal	Active triceps stretch		Shoulder, Elbow, Elbow
Hand Exercises	1	Frontal	Hand functional exercise		Elbow, Wrist, Finger

	2	Frontal	Wrist rotation		Elbow, Wrist, Pinky Finger
Body Position	1	Lateral	Lunge stretch		Ankle, Knee, Hip
	2	Lateral	Seated butterfly stretch		Shoulder, Hip, Knee
	3	Lateral	Flat back exercise		Elbow, Shoulder, Hip
	4	Lateral	Double knee to chest		Shoulder, Hip, Knee

	5	Lateral	Supine knee touch		Shoulder, Hip, Knee
Hip Exercises	1	Lateral	Wall sit		Hip, Knee, Ankle
	2	Lateral	Standing left thigh stretch with wall support		Hip, Knee, Ankle
	3	Lateral	Bent-over deadlift		Shoulder, Hip, Knee

5.4 Medication Adherence Management

5.4.1 Guide patients to complete a weekly medication adherence assessment.^[1]

Below is a line representing your adherence to prescribed endocrine medication over the past week. A score of 0% indicates no medication taken, while 100% indicates full adherence to the prescribed dose. Please mark "√" at the point on the line that best reflects your medication intake.

0%	10%	20%	30%	40%	50%	60%	70%	80%	90%	100%
----	-----	-----	-----	-----	-----	-----	-----	-----	-----	------

5.4.2 The nursing team conducts biweekly telephone follow-ups during the intervention period and monthly telephone follow-ups during the follow-up period.^[7, 8] The specific follow-up content is as follows:

(1) Self-Monitoring and Reporting

- Do you regularly record changes in musculoskeletal symptoms?
Never (0) | Occasionally (1) | Often (2) | Always (3)
- Do you encounter any difficulties or uncertainties when recording?
No (0) | Occasionally (1) | Often (2) | Always (3)
- What was your most recent VAS score (0-10)?
Specify a score (0-10)
- Has there been any change in symptoms?
No change (0) | Slight change (1) | Significant change (2) | Severe change (3)
- What relief measures have you used, and how effective were they?
None (0) | Poor (1) | Moderate (2) | Good (3)
- Have you experienced any new symptoms or worsening of existing symptoms?
No (0) | Slight worsening (1) | Significant worsening (2) | Severe worsening (3)

(2) Diet and Nutrition Management

- Has there been any change in your recent dietary habits?
No change (0) | Slight change (1) | Significant change (2) | Severe change (3)
- Is your daily diet balanced?
Very unbalanced (0) | Unbalanced (1) | Balanced (2) | Very balanced (3)
- Have you been taking supplements?
None (0) | Occasionally (1) | Often (2) | Daily (3)
(Follow up with specific types and dosages of supplements)
- Are there any difficulties or questions regarding dietary management?
None (0) | Slight difficulty (1) | Moderate difficulty (2) | Severe difficulty (3)

(3) Exercise and Rehabilitation

- Do you follow the recommended exercise program?
Never (0) | Occasionally (1) | Often (2) | Always (3)

- Is the frequency and intensity of your exercise appropriate?
Not appropriate (0) | Fairly appropriate (1) | Appropriate (2) | Very appropriate (3)
- Do you experience discomfort or worsening of symptoms after exercise?
No discomfort (0) | Mild discomfort (1) | Moderate discomfort (2) | Severe discomfort (3)
- Do you feel fatigued after exercising?
Never (0) | Occasionally (1) | Often (2) | Always (3)
- Do you need to adjust your exercise plan?
No adjustment needed (0) | Slight adjustment (1) | Moderate adjustment (2) | Major adjustment (3)

(4) Medication Adherence Management

- Do you take your medication on time and at the correct dose?
Never (0) | Occasionally (1) | Often (2) | Always (3)
- Have you missed or incorrectly taken any doses?
No (0) | Occasionally (1) | Often (2) | Always (3)
- Have you experienced any side effects from the medication, and did they impact your adherence?
No side effects (0) | Mild side effects (1) | Moderate side effects (2) | Severe side effects (3)
- Have you interrupted endocrine therapy, and if so, what was the reason?
No interruption (0) | Occasionally (1) | Often (2) | Completely stopped (3)

(5) Referral

- Have any abnormal symptoms or other health issues been detected during monitoring?
None (0) | Mild abnormality (1) | Moderate abnormality (2) | Severe abnormality (3)
- Do you need to consult a doctor or undergo further testing?
No need (0) | Possibly needed (1) | Needed (2) | Urgently needed (3)
(If symptoms worsen or become uncontrollable, a referral to a relevant department is recommended.)

6. Intervention Evaluation

Table 6: Evaluation of Intervention Effectiveness

Assessment	Tools	Baseline T0	Intervention Period			Follow-up Period		
			M1	M2	M3	M4	M5	M6
General Information	Baseline Survey Form							
Biomarker - Bone Density	Dual-Energy X-ray Absorptiometry (DXA) Scanner							
Grip Strength	Digital Hand Grip Dynamometer							
Joint Function	WOMAC, M-SACRAH							
Intervention Implementation Status	Review Indicators							
Practitioner Knowledge, Attitude, and Practice (KAP)	Questionnaire							
System Outcomes	Interview Guide							
Patient Intervention Adherence	Follow-Up Record Form							
Practitioner Compliance Rate	Review Indicator Record Form							

【Biomarker - Bone Density】

At months 0 and 6 of the intervention, bone density will be measured using Dual-Energy X-ray Absorptiometry (DEXA). DEXA is widely recognized as the gold standard for bone density assessment due to its high precision and reliability, making it extensively used in clinical diagnosis and research. The primary measurement sites include the lumbar spine and femoral neck, which reflect bone mineral content and overall bone health.

According to the World Health Organization (WHO) bone density diagnostic criteria^[9], the T-score ranges are as follows:

- Normal: T-score ≥ -1
- Low Bone Mass (Osteopenia): T-score between -1 and -2.5
- Osteoporosis: T-score ≤ -2.5

【Grip Strength】

Grip strength will be measured at months 0, 1, 3, and 6 by the exercise team. This measurement primarily evaluates the forearm flexor and hand muscles, representing forearm muscle strength. An electronic handgrip dynamometer will be used. The subject stands with arms relaxed and hanging down, palms facing the thighs, and the dominant arm (non-surgical side) abducted to a 30-degree angle. The participant grips the dynamometer without swinging the arm, squatting, or allowing the dynamometer to touch the body. Each participant will undergo three assessments, with the highest value used for analysis. A 60-second rest interval is provided between each measurement. Reference standards for grip strength are based on normal values from a large-scale national health survey in China.

Normative values for absolute and relative hand grip strength, stratified by sex and age.

	Male (n = 16 263)								Female (23 392)							
	n	Centiles					Mean	SD	n	Centiles					Mean	SD
		5th	25th	50th	75th	95th				5th	25th	50th	75th	95th		
HGS (kg)																
Age groups																
8-	170	6	8	10	12	16	10.08	2.94	217	4	6	8	10	13	8.14	2.65
10-	211	8	10	13	15	19	13.03	3.64	236	6	9	11.5	14	18	11.65	3.68
12-	237	10	15	18	23	33	19.5	6.74	201	10	14	17	20	24	16.94	4.53
14-	180	16.5	24	28	33.5	40.5	28.46	7.26	185	13	16	20	22	27	19.75	4.35
16-	183	26	31	36	40	48	35.77	6.71	314	15	18	21	24	29	21.52	4.23
18-	212	27	33.5	38	42	51	38.12	7.57	293	16	20	23	26	31	23.19	4.98
20-	1922	30	37	42	48	55	42.46	7.59	2998	16	21	24	28	33	24.44	5.02
30-	2874	30	37	42	47	55	42.12	7.56	4631	18	22	26	29	34	25.55	5.16
40-	4085	28	36	40	46	53	40.75	7.56	6400	16	22	25	28	34	24.96	5.25
50-	3362	26	32	37	42	51	37.61	7.66	4491	14	19	22	26	30	22.34	4.92
60-	2034	20	28	32.15	38	46	32.91	7.32	2521	12	17	20	23	28	19.95	4.76
70-80	731	16	22	27	32	40	27.07	7.15	820	10	14	17	20	25	17.31	4.75
Overall	16 201	20	32	38	44	52	37.72	9.67	23 307	14	20	23	27	32	23.23	5.80

Figure 2: Reference Standard for Grip Strength

【Audit Record Table】

Table 7: Audit Record Table

Serial Number	Audit criteria	Compliance Status	Remarks
1	The nurse assesses the patient's risk of MS, informs the relevant risk factors, and records them.	 Compliant  Non-compliant	
2	The nurse uses a professional scale to assess the MS.	 Compliant	

		 Non-compliant
3	The doctor tests the patient's bone mineral density once a year and gives treatment when appropriate.	 Compliant  Non-compliant
4	The nurse instructs the patient to take calcium and vitamin D supplements.	 Compliant  Non-compliant
5	The nurse delivers the patient health education about MS.	 Compliant  Non-compliant
6	The doctor prescribes acetaminophen or non-steroidal anti-inflammatory drugs, traditional Chinese medicine, acupuncture, night splinting other treatments when appropriate.	 Compliant  Non-compliant
7	The nurse instructs the patient to participate in exercise.	 Compliant  Non-compliant
8	The nurse regularly monitors patients for MS.	 Compliant  Non-compliant

7. Intervention Flowchart

[figure not shown]

Figure 3: Intervention Flowchart

8. Research Schedule

Table 8: Intervention and Follow-Up Schedule for Managing Musculoskeletal Symptoms in Breast Cancer Patients

	Phase	Duration	Follow-Up Frequency
1	Intervention Initiation	November 2024 - December 2024	/
2	Intervention Period	3 months	Weekly Telephone Follow-Up
3	Follow-Up Period	3 months	Biweekly Telephone Follow-Up

9. Appendix

9.1 Baseline Survey Form - Musculoskeletal Symptom Form

Dear Patients,

In order to better understand your condition during endocrine therapy and to help us provide you with appropriate treatment and care, we have designed the following questionnaire to assess your physical and psychological status. The information you provide will serve as a valuable reference for clinical medical and nursing work. We kindly ask that you fill out the questionnaire thoroughly, reflecting your true situation. Some questions may be completed by medical personnel on your behalf.

We sincerely thank you for your participation, support, and cooperation!

- *There are no right or wrong answers. Please respond based on how you usually feel and act.*
- *Please fill out the form based on your actual situation.*
- *For items with a ☐, please place a "✓" in the appropriate box.*

☐ **Outpatient** ☐ **Inpatient**

Outpatient/Inpatient Number: _____

Enrollment/Follow-up Date: _____

Investigator's Signature: _____

I. General Information

1. Gender:

☐ Male ☐ Female

2. Age: _____ years

3. Height: _____ cm Weight: _____ kg

4. Religious Belief:

☐ None ☐ Buddhism ☐ Christianity ☐ Islam ☐ Other

5. Do you regularly participate in religious activities or prayer?

☐ Never ☐ Occasionally ☐ Sometimes ☐ Frequently

6. How much does your religious belief influence your lifestyle?

☐ No influence ☐ Slight influence ☐ Some influence ☐ Significant influence

7. Educational Level:

☐ Primary school or below
☐ Middle school
☐ Technical school/High school
☐ College/University
☐ Graduate degree or higher

8. Employment Status:

☐ Unemployed ☐ Part-time job ☐ Full-time job ☐ Retired ☐ Homemaker

9. Marital Status:

☐ Single ☐ Married ☐ Divorced ☐ Widowed

10. Living Situation:

☐ Stable ☐ Unstable ☐ Homeless

11. Medical Expenses:

☐ Fully self-paid
☐ Mostly self-paid
☐ Partially self-paid
☐ No self-payment

12. Economic Pressure:

☐ None ☐ Slight ☐ Some ☐ Significant

13. Understanding of your disease:

☐ Not at all ☐ Slightly ☐ Somewhat ☐ Very well

II. Medical History

1. Diagnosis Date: _____ Year _____ Month

2. Surgical Approach: _____

3. Pathological Type: _____ (e.g., ductal carcinoma, lobular carcinoma, ductal carcinoma in situ, lobular carcinoma in situ, inflammatory breast cancer, mucinous carcinoma, medullary carcinoma) (may consult healthcare professionals for completion)

4. Comprehensive Treatment Plan:

☐ Chemotherapy: _____ ☐ Radiotherapy: _____
☐ Targeted Therapy: _____ ☐ Other: _____

5. Tumor Stage:

☐ Stage 0 ☐ Stage I ☐ Stage II ☐ Stage III ☐ Stage IV ☐ Unclear

6. Endocrine Therapy Medication Currently Administered (please specify the detailed regimen on the line below): _____

Start Date of Endocrine Therapy: _____

☐ Anastrozole ☐ Letrozole
☐ Exemestane ☐ Ovarian function suppression medication
☐ Other: _____

7. Do you have any other chronic diseases? (select all that apply):

☐ Hypertension ☐ Diabetes ☐ Coronary heart disease
☐ Other: _____ ☐ None

III. Menstrual and Fertility Status

1. Time Since Last Menstruation: _____ years (If within one year, fill in 0.5 years)

IV. Dietary Habits and Nutrition

(1) Dietary Habits and Nutrition

1. Do you take dietary supplements (e.g., fish oil, calcium tablets, vitamin D, etc.)?

☐ Yes, type and dosage: _____ ☐ No

(2) Behavioral Habits

1. Do you smoke?

☐ Yes ☐ Used to, but quit ☐ No

2. Do you drink alcohol?

☐ Yes ☐ Used to, but quit ☐ No

3. Exercise frequency:

☐ Daily ☐ 3-4 times per week ☐ 1-2 times per week ☐ Rarely exercise

4. Exercise intensity:

☐ Light activity ☐ Moderate activity ☐ Intense activity

(3) Sleep Situation

1. Sleep quality in the past month:

☐ Very good ☐ Fairly good ☐ Fairly poor ☐ Very poor

V. Medication Adherence

The following line represents **how closely you followed your prescribed medication regimen in the past week.** 0% means you did not take any medication, and 100% means you took the full amount as prescribed. Please place a "√" on the line at the point that best reflects your adherence.

0%	10%	20%	30%	40%	50%	60%	70%	80%	90%	100%
----	-----	-----	-----	-----	-----	-----	-----	-----	-----	------

VI. Symptom Assessment

Type of Musculoskeletal Symptoms: _____

Please rate the musculoskeletal symptoms you are experiencing using the VAS score. Mark "√" at the point on the line that best reflects your symptom score. (Note: VAS score ranges from 0 to 10, where 0 indicates no pain and 10 indicates severe pain.)

0	1	2	3	4	5	6	7	8	9	10
---	---	---	---	---	---	---	---	---	---	----

Hand Symptoms and Function Assessment

Please select your answers based on your actual situation in the past 48 hours (with scores increasing from 0 to 100):

1. Pain experienced while inactive:

☐0 ☐10 ☐20 ☐30 ☐40 ☐50 ☐60 ☐70 ☐80 ☐90 ☐100

2. Pain experienced during intense work:

☐0 ☐10 ☐20 ☐30 ☐40 ☐50 ☐60 ☐70 ☐80 ☐90 ☐100

3. Severity of stiffness upon waking in the morning:

☐0 ☐10 ☐20 ☐30 ☐40 ☐50 ☐60 ☐70 ☐80 ☐90 ☐100

4. Severity of stiffness after sitting, lying down, or resting:

☐0 ☐10 ☐20 ☐30 ☐40 ☐50 ☐60 ☐70 ☐80 ☐90 ☐100

5. Difficulty in opening/closing doors:

☐0 ☐10 ☐20 ☐30 ☐40 ☐50 ☐60 ☐70 ☐80 ☐90 ☐100

6. Difficulty in buttoning/unbuttoning clothes:

☐0 ☐10 ☐20 ☐30 ☐40 ☐50 ☐60 ☐70 ☐80 ☐90 ☐100

7. Difficulty in turning a faucet on/off:

☐0 ☐10 ☐20 ☐30 ☐40 ☐50 ☐60 ☐70 ☐80 ☐90 ☐100

8. Difficulty in pulling up/down a zipper:

☐0 ☐10 ☐20 ☐30 ☐40 ☐50 ☐60 ☐70 ☐80 ☐90 ☐100

9. Difficulty in tying shoelaces:

☐0 ☐10 ☐20 ☐30 ☐40 ☐50 ☐60 ☐70 ☐80 ☐90 ☐100

10. Difficulty in opening a jar:

☐0 ☐10 ☐20 ☐30 ☐40 ☐50 ☐60 ☐70 ☐80 ☐90 ☐100

11. Difficulty in turning pages of a newspaper:

☐0 ☐10 ☐20 ☐30 ☐40 ☐50 ☐60 ☐70 ☐80 ☐90 ☐100

12. Difficulty in writing:

☐0 ☐10 ☐20 ☐30 ☐40 ☐50 ☐60 ☐70 ☐80 ☐90 ☐100

Knee and Hip Joint Symptoms and Function Assessment

Please select your answers based on your actual situation in the past 48 hours (with scores increasing from 0 to 100):

1. Intensity of knee or hip pain while ambulating on a flat surface:

☐0 ☐10 ☐20 ☐30 ☐40 ☐50 ☐60 ☐70 ☐80 ☐90 ☐100

2. Intensity of knee or hip pain during stair ascent or descent:
☐0 ☐10 ☐20 ☐30 ☐40 ☐50 ☐60 ☐70 ☐80 ☐90 ☐100
3. Intensity of knee or hip pain during nocturnal rest:
☐0 ☐10 ☐20 ☐30 ☐40 ☐50 ☐60 ☐70 ☐80 ☐90 ☐100
4. Intensity of knee or hip pain while seated or in a supine position:
☐0 ☐10 ☐20 ☐30 ☐40 ☐50 ☐60 ☐70 ☐80 ☐90 ☐100
5. Intensity of knee or hip pain while in an upright position:
☐0 ☐10 ☐20 ☐30 ☐40 ☐50 ☐60 ☐70 ☐80 ☐90 ☐100
6. Severity of stiffness in the knee or hip upon waking in the morning:
☐0 ☐10 ☐20 ☐30 ☐40 ☐50 ☐60 ☐70 ☐80 ☐90 ☐100
7. Severity of stiffness in the knee or hip following periods of sitting or rest during the day:
☐0 ☐10 ☐20 ☐30 ☐40 ☐50 ☐60 ☐70 ☐80 ☐90 ☐100
8. Difficulty experienced during stair ascent:
☐0 ☐10 ☐20 ☐30 ☐40 ☐50 ☐60 ☐70 ☐80 ☐90 ☐100
9. Difficulty experienced during stair descent:
☐0 ☐10 ☐20 ☐30 ☐40 ☐50 ☐60 ☐70 ☐80 ☐90 ☐100
10. Difficulty in transitioning from a seated to a standing position:
☐0 ☐10 ☐20 ☐30 ☐40 ☐50 ☐60 ☐70 ☐80 ☐90 ☐100
11. Difficulty while maintaining an upright position
☐0 ☐10 ☐20 ☐30 ☐40 ☐50 ☐60 ☐70 ☐80 ☐90 ☐100
12. Difficulty in bending forward to reach the ground
☐0 ☐10 ☐20 ☐30 ☐40 ☐50 ☐60 ☐70 ☐80 ☐90 ☐100
13. Difficulty while ambulating on a flat surface
☐0 ☐10 ☐20 ☐30 ☐40 ☐50 ☐60 ☐70 ☐80 ☐90 ☐100
14. Difficulty in entering and exiting a vehicle or boarding a bus
☐0 ☐10 ☐20 ☐30 ☐40 ☐50 ☐60 ☐70 ☐80 ☐90 ☐100
15. Difficulty experienced during shopping activities
☐0 ☐10 ☐20 ☐30 ☐40 ☐50 ☐60 ☐70 ☐80 ☐90 ☐100
16. Difficulty in donning socks
☐0 ☐10 ☐20 ☐30 ☐40 ☐50 ☐60 ☐70 ☐80 ☐90 ☐100
17. Difficulty in doffing socks
☐0 ☐10 ☐20 ☐30 ☐40 ☐50 ☐60 ☐70 ☐80 ☐90 ☐100
18. Difficulty in rising from a supine position in bed
☐0 ☐10 ☐20 ☐30 ☐40 ☐50 ☐60 ☐70 ☐80 ☐90 ☐100
19. Difficulty while lying in bed
☐0 ☐10 ☐20 ☐30 ☐40 ☐50 ☐60 ☐70 ☐80 ☐90 ☐100
20. Difficulty in exiting a bathtub or bathroom
☐0 ☐10 ☐20 ☐30 ☐40 ☐50 ☐60 ☐70 ☐80 ☐90 ☐100
21. Difficulty in transitions between sitting and standing
☐0 ☐10 ☐20 ☐30 ☐40 ☐50 ☐60 ☐70 ☐80 ☐90 ☐100

☐0 ☐10 ☐20 ☐30 ☐40 ☐50 ☐60 ☐70 ☐80 ☐90 ☐100

22. Difficulty in rising from a toilet seat

☐0 ☐10 ☐20 ☐30 ☐40 ☐50 ☐60 ☐70 ☐80 ☐90 ☐100

23. Difficulty in performing heavy household chores

☐0 ☐10 ☐20 ☐30 ☐40 ☐50 ☐60 ☐70 ☐80 ☐90 ☐100

24. Difficulty in performing light household chores

☐0 ☐10 ☐20 ☐30 ☐40 ☐50 ☐60 ☐70 ☐80 ☐90 ☐100

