1. To unlock the front door with a key?

No difficulty _____ Impossible

2. To button or unbutton buttons?

No difficulty _____ Impossible

3. To turn on the faucet?

No difficulty _____ Impossible

4. To zip or unzip a zipper?

No difficulty _____ Impossible

5. To tie shoelaces?

No difficulty _____ Impossible

6. To unscrew and screw on the toothpaste cap?

No difficulty _____ Impossible

7. To turn the pages of the newspaper?

No difficulty _____ Impossible

8. To write by hand?

No difficulty _____ Impossible

PART 2: STIFFNESS

Think about the **stiffness** (not pain) you have had in the past 48 hours because of your **finger joint problems**. Joint

stiffness is normally experienced as a **limitation or reduction in the mobility of your joints**.

(Please mark each answer with an “X” on the line.)

QUESTION:

9. How **severe** was your joint stiffness **after you first woke up** in the morning?

No stiffness _____ Unbearable stiffness

10. How **severe** was your joint stiffness later in the day after your hands had been at rest for a while?

No stiffness _____ Unbearable stiffness

PART 3: PAIN

Think about the pain you have had in the past 48 hours because of your finger joint problems.

(Please mark each answer with an “X” on the line.)

QUESTION: How severe was your pain...

11. During your work activities or difficult house chores?

No pain _____ Unbearable pain

12. When your hands were at rest in the evening?

No pain _____ Unbearable pain

9.5 Questionnaire on Nurses' Knowledge, Beliefs, and Practices Regarding the Management of Musculoskeletal Symptoms in Breast Cancer Patients

Undergoing Endocrine Therapy in a Multicultural Context

We are conducting a study on the differences in nurses' knowledge, attitudes, and practices regarding the management of musculoskeletal symptoms in breast cancer patients undergoing endocrine therapy in a multicultural context. We sincerely invite you to participate in this research. If you agree to take part, you will be asked to complete a four-part questionnaire, which is expected to take approximately 15-20 minutes. Your participation will greatly contribute to our understanding and improvement of the quality of care for breast cancer patients.

There are no known risks associated with this study. All data collected will be anonymized and kept strictly confidential. You are free to withdraw from the study at any time without providing any reason. We greatly appreciate your support and participation.

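### The protocol contains two non-identical 12-item hand questionnaires (the hand block in 9.1 and the M-SACRAH in 9.3) and does not say which is scored as the M-SACRAH outcome

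*Protocol*

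**What the plan says.** Table 6 (Protocol, section 6) lists "WOMAC, M-SACRAH" as the tools for joint function. A separate row of that table gives the Baseline Survey Form as the tool for general information.

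Section 9.3 prints the M-SACRAH: eight function items, two stiffness items and two pain items. The introduction to each of the three parts attributes the symptom to the finger joints. The pain part, for example, opens with "Think about the pain you have had in the past 48 hours because of your finger joint problems". The rest-stiffness item asks about "joint stiffness later in the day after your hands had been at rest for a while". Answers are marks on a line with a verbal label at each end.

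Section 9.1 is the form that patients fill in. Under Symptom Assessment it has a block headed "Hand Symptoms and Function Assessment", also with 12 items and a 48-hour recall. Its introduction mentions no finger joints. Its items include "Pain experienced while inactive", "Severity of stiffness after sitting, lying down, or resting" and "Difficulty in opening a jar". Answers are tick boxes from 0 to 100 in steps of 10. A separate knee and hip block follows. The date field at the top of the form serves both enrolment and follow-up.

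Section 3.1 names WOMAC as the primary measurement tool.

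**The concern.** The two hand questionnaires are close enough that the 9.1 block was evidently meant as the M-SACRAH, yet they are not the same instrument. The protocol does not say which one supplies the Table 6 outcome, nor whether one version is used throughout.

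Two things are at stake. The first is what the hand score measures. Eligibility (section 4.2.1) requires musculoskeletal symptoms from endocrine therapy, not hand symptoms, so patients troubled only at the knee or hip can enrol and will answer the hand block. An item that names no site leaves room for them to report those symptoms there. The second is whether baseline and follow-up values are on the same scale.

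M-SACRAH is the only hand-specific patient-reported instrument in Table 6. WOMAC, as described in 9.2, covers the hip and knee, and grip strength is a performance measure.

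**Working it through.** No stated figure has to be reproduced here. The check is an item-by-item comparison of the two questionnaires.

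**Structure**

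| Feature | 9.3 M-SACRAH | 9.1 hand block |
|---|---|---|
| Items | 8 function + 2 stiffness + 2 pain = 12 | 2 pain + 2 stiffness + 8 function = 12 |
| Recall | 48 hours | 48 hours |
| Attribution | finger joints, in all three parts | none in stem or items; block heading says hand |
| Response | mark on a line, labelled ends | 11 boxes, 0 to 100, no end labels |

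**Function items.** Buttons, faucet, zipper, shoelaces, newspaper and writing match: 6 of 8. Two tasks differ. Unlocking a door with a key becomes opening and closing doors, and "To unscrew and screw on the toothpaste cap" becomes "Difficulty in opening a jar". That is 2/8 = 25%.

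**Pain and stiffness items**

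| 9.3 | 9.1 | Change beyond the lost attribution |
|---|---|---|
| Stiffness on first waking | Stiffness on waking | none of substance |
| Later stiffness, hands at rest | After sitting, lying or resting | hands replaced by whole-body postures |
| Pain in work or hard chores | Pain in intense work | reworded |
| Evening pain, hands at rest | Pain while inactive | hands and time of day dropped |

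None of the four 9.1 items names a body site: 4/12 = 33% of the block, and all of its pain and stiffness content. Three of the four are also reworded. With the two function tasks, 3 + 2 = 5 of 12 items (42%) differ in content as well as attribution.

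**Contrast within the same form.** In the knee and hip block, all seven pain and stiffness items (five pain, two stiffness) name the knee or hip. The missing site is therefore particular to the hand block. The knee and hip item on stiffness after sitting or rest is close in wording to hand item 4, which makes item 4 the most open to non-hand symptoms.

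**What follows under each reading of the protocol**

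1. 9.1 is scored throughout: the outcome is an altered M-SACRAH.
2. 9.1 is used at baseline and 9.3 at follow-up: change from baseline subtracts one questionnaire from another.
3. Both are given at the same visit: patients complete two differing hand forms, and nothing says which counts.
4. 9.3 is scored throughout and 9.1 is only descriptive: the outcome is intact, but the protocol does not say so, and the baseline form still carries a second hand questionnaire.

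Each reading needs a correction or a clarifying statement.

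**The case against.** A reader might infer that the hand outcome simply is not the M-SACRAH. The documents do not support that. Table 6 names M-SACRAH, 9.3 prints it in full, and Table 6 places the Baseline Survey Form under general information. No passage says that the 9.1 block replaces 9.3. The follow-up date field and the matching 8/2/2 structure make that use plausible but do not settle it.

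A reader might also infer that all four pain and stiffness items will pick up knee, hip or whole-body symptoms. That is a risk and is not shown. The block heading directs the patient to the hand, and knee and hip symptoms have their own block immediately afterwards. The risk is clearest for item 4 and weaker for the other three. It cannot be sized: the documents contain no response data, and 9.3 gives no scoring rule.

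Nor do the documents show that a treatment effect would be diluted. Nothing suggests that the form differs by arm, so misplaced symptoms would tend to enter both arms. The exercise programme also covers the shoulder, hip, leg and back, so picking up those symptoms need not shrink the difference between arms. Likewise, if the instrument changed after baseline in both arms alike, randomisation would still protect the between-arm comparison at follow-up. The within-patient change would be what loses its meaning.

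The missing end labels are a small matter, because the stem does say that scores rise from 0 to 100. Some of the wording may come from translation, and the versions that patients see are not in the protocol. Translation would not readily explain a jar in place of a toothpaste cap.

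What stands after all this is the inconsistency itself: two different hand questionnaires and no statement of which is scored.

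**Conclusion.** The point holds as an inconsistency in the outcome definition. The 9.1 block and the 9.3 M-SACRAH share their item count, domains and recall period. They differ in attribution (dropped from the stem, leaving 4 of 12 items with no site), in two of eight function tasks, in the wording of three of four pain and stiffness items, and in the response labels. The protocol fixes neither which one is the Table 6 outcome nor that one version is used throughout.

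The consequence is conditional. Scoring 9.1 gives a modified M-SACRAH, whose comparability with the 9.3 instrument cannot be assumed without validation data, and the protocol gives none. Mixing the versions makes change from baseline uninterpretable as a change on one scale. This assumes that the English text in 9.1 and 9.3 reflects what patients are given.

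The severity is minor. WOMAC is the primary tool, so the sample size in section 3.1 (26 per group, 33 after attrition) is untouched.

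**What to change.** Replace the 12 hand items in 9.1 with the 9.3 items, together with the finger-joint stem and the end labels. State in section 6 that this single version is the M-SACRAH outcome and is used at every assessment at all three sites.

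For patients who have already completed the present 9.1 block, keep that version for all their assessments and report it as a modified, study-specific hand questionnaire, not as the M-SACRAH.

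The cost is revising one page of the form and its translations. The number of items stays at 12. An analysis plan alone cannot repair this, because it cannot restore an attribution that patients were not shown.
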